9.5.25. Rate of Urinary Tract Infections (UTIs) Reported as Adverse Events

The rate of UTIs beginning at least 3 days after the start of study drug treatment through Week 16 (**H₈**) reported as adverse events will be analyzed in the same manner as described in [9.4.2 above](#).

Summary statistics will be presented along with a full data listing by treatment group.

9.5.26. Percentage of Subjects with One or more UTIs Reported as Adverse Events.

The percentage of subjects with 1 or more UTIs reported as adverse events beginning at least 3 days after the start of study drug treatment through Week 16 will be analyzed in the same manner as the primary efficacy endpoint analysis described in [9.3.1 above](#).

Summary statistics will be presented along with a full data listing by treatment group.

9.5.27. Percentage of Subjects with Expanded-Definition Clinically Symptomatic Respiratory Illness (with or without an associated laboratory-confirmed pathogen) by Week 16

Percentage of subjects with expanded-definition clinically symptomatic respiratory illness (with or without an associated laboratory-confirmed pathogen) beginning at least 3 days after the start of study drug treatment by Week 16 will be analyzed as an exploratory analysis. Expanded-definition clinically symptomatic respiratory illness is defined similarly to the primary endpoint except the general symptoms of body aches and lack of energy will be included in the list of general symptoms for the purpose of identifying a case of an expanded CSRI.

The analysis method will be the same as the primary endpoint efficacy analysis as described in [9.3.1 above](#).

Summary statistics will be presented along with a full data listing by treatment group.

9.6. Additional Sensitivity/Exploratory Analyses

9.6.1. Percentage of Subjects with One or More Clinically Symptomatic Respiratory Illnesses Associated with ≥ 1 Laboratory-confirmed Pathogen(s) Including Assessment using Midturbinate Swabs

The percentage of subjects with CSRI(s) associated with ≥ 1 laboratory-confirmed pathogen(s) beginning at least 3 days after the start of study drug treatment through Week 16 as assessed by pre-specified clinical diagnostic criteria and respiratory pathogen PCR of nasopharyngeal swabs or midturbinate swabs,

This document is confidential.

sputum gram stain and culture and/or RIDTs will be analyzed in the same manner as the primary efficacy analysis as described in 9.3.1 above.

Laboratory results from a specimen obtained within 3 days before the CSRI start date through the CSRI end date will be used to determine if the CSRI is associated with ≥ 1 laboratory-confirmed pathogen. Laboratory confirmation includes a positive respiratory pathogen PCR of nasopharyngeal swabs, sputum gram stain and culture, RIDT, and/or respiratory pathogen PCR of midturbinate swabs. If multiple specimens are obtained for a particular CSRI, then any positive result will be counted as laboratory confirmation if it occurs within 3 days before the CSRI start date through the CSRI end date. A laboratory-confirmed CSRI may be associated with multiple pathogens.

9.6.2. Rate of Clinically Symptomatic Respiratory Illness Associated with ≥ 1 Laboratory-confirmed Pathogen(s) Including Assessment using Midturbinate Swabs

The rate of CSRI associated with ≥ 1 laboratory-confirmed pathogen(s) beginning at least 3 days after the start of study drug treatment through Week 16 as assessed by pre-specified clinical diagnostic criteria and respiratory pathogen PCR of nasopharyngeal swabs or midturbinate swabs, sputum gram stain and culture and/or RIDTs will be analyzed in the same manner as described in 9.4.2 above. 9.6.1 describes which laboratory result will be used to determine if the CSRI is associated with ≥ 1 laboratory-confirmed pathogen.

Summary statistics will be presented along with a full data listing by treatment group.

This document is confidential.

10. Safety

Safety analyses will be conducted on the Safety Set (SAF) and will be assessed on the basis of adverse event (AE), clinical laboratory data, ECG parameters, physical examinations, and vital signs.

10.1. Extent of Exposure

Duration of exposure is defined as (Date of Last Dose – Date of First Dose) +1. If date of last dose is unknown then the date of last clinical visit no later than the Week 16 Visit will be used to impute the date of last dose. If there are temporary dose interruptions based on the data from the eCRF, then only the periods of time when study drug interruption did not occur will be used to calculate the duration of exposure. Duration of exposure will be summarized using descriptive statistics by treatment group. The duration of exposure (in days) will also be categorized as follows: <7, 7-<14, 14-<28, 28-<42, 42-<46, 56-<70, 70-<84, 84-<98, 98-<112, ≥112, and tabulated by treatment group..

A listing including study drug administration information from the eDiary will be presented.

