5.5.2. Discontinuation of Study Treatment

Premature discontinuation of study treatment for a subject occurs when study drug is permanently stopped earlier than the protocol planned duration, and can be initiated by either the subject, the Investigator, or the Sponsor.

Study treatment must be permanently discontinued under the following circumstances:

- Subject decision-subjects may choose to discontinue study drug treatment for any reason at any time.
- The Investigator believes that continuation of study treatment would negatively impact the safety of the subject or the risk/benefit ratio of trial participation. This includes any laboratory abnormalities that in the judgment of the Investigator, taking into consideration the subject's overall status, prevents the subjects from continuing participation in the study.
- Any protocol deviation that results in a significant risk to the subject's safety.
- Emergence of the following AEs:
 - Hypersensitivity reaction to study drug
 - Gastrointestinal SAE
 - Oral ulcers, stomatitis, or diarrhea that limits oral intake or is associated with dehydration or weight loss (>2% from Baseline weight) over two or more consecutive study visits
 - Cardiac SAE (including, but not limited to, MI and unstable angina)
 - Study drug-related non-infectious pneumonitis (see [Section 13.2](#) [Appendix 2])
- Subject whose treatment has been unblinded.

If premature discontinuation of study treatment occurs, Investigator must determine the primary reason for the subject's premature discontinuation of study treatment and record this information on the CRF. Subjects who permanently discontinue study drug due to an AE should return to the study site as soon as possible for an unscheduled visit to return all study drug for reconciliation and accountability and to have the following assessments: vital signs, complete physical exam, and blood and urine collection for safety labs. Subjects who discontinue treatment for reasons other than an AE should return all study drug for reconciliation and accountability at the next study visit. UNLESS subjects withdraw their consent (see [Section 5.5.3](#)), they should return for all remaining study visits (including completing the daily eDiary). If they fail to return for these assessments for unknown reasons, every effort (e.g., telephone, e-mail, certified letter) should be made to contact the subject as specified in [Section 5.5.4](#) (Lost to follow-up).

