6.10. Other Assessments

6.10.1. Subject-Reported Outcomes Assessments

Subject-Reported Study Drug Administration

Subjects will report the time of their daily study drug administration each day in an eDiary. This information will be used to assess treatment compliance together with pill count (per section 5.4). Further details are provided in the SAP.

Subject-Reported Health Outcomes/Quality of Life

The EuroQol-5 Dimensions-5 Levels (EQ-5D-5L) will be administered at the Baseline Visit and the Week 16 Visit. In addition, subjects will be prompted in their eDiary to complete the EQ-5D-5L each day that they report experiencing one or more respiratory illness symptoms in their eDiary through Week 16.

EQ-5D-5L is a standardized measure of health status developed by the EuroQol Group in order to provide a simple, generic measure of health for clinical and economic appraisal (see [Section 13.3](#) [Appendix 3]). The EQ-5D-5L questionnaire consists of 2 pages: the EQ-5D-5L descriptive system and the EQ visual analogue scale (VAS). The descriptive system comprises 5 dimensions (mobility, self-care, usual activities, pain/discomfort, and anxiety/depression), each of which is divided into 5 levels. The EQ VAS records the patient's self-rated health on a 20-cm vertical visual analogue with "the best health you can imagine" as 100 and "the worst health you can imagine" as 0.

Further information is provided in the SOM and the SAP.

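### SAP 10.1 leaves exposures of 46 to 55 days without a band, and its fallback for an unknown last-dose date has no cap at treatment discontinuation

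*SAP*

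**What the plan says.** SAP 10.1 gives the formula: "Duration of exposure is defined as (Date of Last Dose – Date of First Dose) +1". For a missing last dose it adds: "If date of last dose is unknown then the date of last clinical visit no later than the Week 16 Visit will be used". Temporary interruptions recorded on the eCRF are taken out: "only the periods of time when study drug interruption did not occur will be used to calculate the duration of exposure". The results are reported in two ways. One is continuous: "Duration of exposure will be summarized using descriptive statistics by treatment group". The other is a tabulation in the bands "<7, 7-<14, 14-<28, 28-<42, 42-<46, 56-<70, 70-<84, 84-<98, 98-<112, ≥112". Both feed the Extent of Exposure table (14.3.4.4, Safety Set).

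Protocol 5.5.2 separates stopping drug from leaving the study. Unless subjects who stop treatment withdraw consent, "they should return for all remaining study visits (including completing the daily eDiary". Protocol 6.10.1 describes the dosing record: "Subjects will report the time of their daily study drug administration each day in an eDiary". Protocol 5.4 adds pill counts at study visits, and 5.5.2 requires drug to be returned after an early stop.

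**The concern.** The bands are meant to partition exposure time, but the upper limit of one does not meet the lower limit of the next. A subject whose duration falls between them cannot be placed.

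The fallback date suits a trial in which stopping drug means leaving: the last visit is then close to the last dose. Here a subject can stop drug in week 3 and still attend through Week 16. If that subject's last-dose date is missing, the rule selects the Week 16 visit and the subject looks like a completer. The interruption clause does not help, because it deals with temporary gaps and this stop is permanent.

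At stake is the accuracy of the table against which the safety data at 10 mg are read, particularly for subjects who stopped early.

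**Working it through.** **Bands.** Placing every whole-day duration from 1 to 129 in the listed bands leaves exactly ten values uncovered: 46, 47, 48, 49, 50, 51, 52, 53, 54 and 55. Reading 42-<46 as 42-<56 leaves none.

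The gap can be reached from the trial's own schedule. Inputs: baseline is Day 0 and visits have a window of ±5 days (Protocol Table 6-1); the first dosing day is study day 1 (SAP 7.2.3). A last dose dated to the Week w visit gives an exposure of 7w + 1 days, ±5.

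- Week 6: 43 days, range 38 to 48, of which 46 to 48 have no band.
- Week 8: 57 days, range 52 to 62, of which 52 to 55 have no band.

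So the fallback rule can itself produce durations that the table cannot show.

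**Fallback date, subject who stops drug but stays in the study.** An on-time Week 16 visit falls on study day 7 × 16 + 1 = 113, so credited exposure is (113 − 1) + 1 = 113 days, or 108 to 118 with the window. Most of that range lies in the top band (≥112); 108 to 111 lies in the band below it. The overstatement is 113 minus the true duration:

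| True exposure (days) | Credited (days) | Excess (days) |
|---|---|---|
| 14 | 113 | 99 |
| 21 | 113 | 92 |
| 28 | 113 | 85 |
| 84 | 113 | 29 |

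**Fallback date, subject who leaves the study between visits.** With on-time visits, the last one attended comes before the last dose and the error changes sign:

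| True exposure (days) | Last visit attended | Credited (days) | Error (days) |
|---|---|---|---|
| 28 | Week 2 | 15 | −13 |
| 56 | Week 6 | 43 | −13 |
| 84 | Week 8 | 57 | −27 |

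**Effect on an arm mean.** The documents do not say how many last-dose dates will be unknown. As an assumption, let a share f of an arm of 533 be stoppers with an unknown date, true exposure 28 days, all attending Week 16 on time. The mean then rises by f × (113 − 28) = 85f days:

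- f = 0.5% (about 3 subjects): +0.4 day
- f = 1% (about 5): +0.9 day
- f = 2% (about 11): +1.7 days
- f = 5% (about 27): +4.3 days

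**The case against.** The best reply is that the rule should rarely be triggered. If the daily dosing diary shows when drug stopped, the date is not unknown. SAP 7.2.2 already uses diary dosing entries to decide whether a subject was treated and to fix the first-dose date, and SAP 10.1 lists the diary dosing data. Subjects who stop for an adverse event are the best documented: Protocol 5.5.2 asks them back as soon as possible to return drug, and the reason for stopping goes on the CRF. Nor must every stopper who stays in the study attend Week 16 in person, since 5.5.2 accepts telephone contact as part of the minimum follow-up.

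This stands as an argument that few subjects are affected. It does not repair the rule. SAP 10.1 names no source for the last-dose date, so it does not say that the diary is consulted before the clinic visit is used. Diaries can also lapse: SAP 9.3.2.2 plans to tabulate runs of missing entries up to 105 days or more.

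On the bands, 42-<46 is an evident slip for 42-<56, and routine checking should expose rows that do not sum. That is fair, but the SAP is the text from which the table will be programmed.

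A reader might infer more than the documents support:

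- *Early stoppers in general get near-full exposure, so the table as a whole is wrong.* No. Over-crediting needs an early stop, an unknown date and attendance at Week 16, all together. The band gap touches only the categorical rows.
- *The error always inflates exposure and makes the arms look alike.* No. For subjects who leave between visits it runs the other way.
- *Hypothesis tests are affected.* SAP 9.4.2 puts an offset for length of treatment exposure in the rate models, but does not say that the offset uses the 10.1 duration. Protocol 9.4.3.4 plans no formal inference on safety, and its adverse-event percentages are based on numbers of subjects.

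**Conclusion.** Both errors are real, and both are small. The band gap is certain: ten day-values, 46 to 55, have no category, while the descriptive statistics on continuous duration are untouched. The fallback rule gives a wrong value for a specific group: stoppers with an unknown last-dose date who stay on the visit schedule. For them the individual error can be large (92 days for a day-21 stop with an on-time Week 16 visit). The number affected is not given and is probably small. Under the assumptions in the working, the shift in an arm mean is under 1 day if 1% or fewer are affected. The documents support neither a claim of one-directional bias nor one of an effect on any test.

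**What to change.** In SAP 10.1:

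1. Change 42-<46 to 42-<56.
2. For subjects with a recorded permanent treatment discontinuation and an unknown last-dose date, impute the last eDiary dosing entry. If the diary had lapsed before the stop, use pill-count or drug-accountability data, because the last entry alone would understate exposure in someone who kept dosing. In either case the imputed date must not be later than the recorded discontinuation or drug-return date.
3. Keep the last clinic visit, no later than Week 16, only for subjects with no record of stopping treatment. Take the last eDiary dosing entry instead if it is later.

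The cost is a few lines of SAP text and derivation code. The diary, pill-count and drug-return data are already collected.

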10.2. Treatment Compliance

Treatment compliance will be summarized as the number (%) of subjects indicated as compliant (≥80%) on the eCRF by treatment group.

Subjects are expected to take 1 tablet of study medication once per day through the Week 16 visit.

10.3. Adverse Events

An adverse event is any untoward medical occurrence associated with the use of a drug in humans, whether or not considered drug-related. All adverse events (AEs) will be coded using the MedDRA version 22.0 or higher. Only treatment-emergent adverse events, defined as any adverse events that start or increase in intensity on or after the first dose of double-blind treatment (Study Day 1), were collected in this study. The following listings of AEs will be provided by subjects:

- All AEs,
- Serious adverse events (SAEs)
- AEs leading to death
- AEs leading to study withdrawal
- AEs leading to study drug discontinuation
- Severe AEs
- Study drug related AEs
- Study drug related SAEs

Adverse Events will be included in summary tables by treatment received. An overall summary table of AEs through Week 20 will be produced for the following categories:

This document is confidential.

- Any AE
- Grade 1 (Mild) AEs, Grade 2 (Moderate) AEs, Grade 3 (Severe) AEs, Grade 4 (Severe and Life Threatening), and Grade 5 (Fatal) AEs
- Study drug-related AEs
- Serious AEs
- Study drug-related Serious AEs
- AEs leading to permanent study drug discontinuation
- AEs leading to study discontinuation
- AEs leading to death

All AEs will be classified by SOC and PT. Frequency count of AEs, the number of unique subjects experiencing an AE, percentage of unique subjects experiencing an AE and total number of events will be tabulated by treatment. For the number of unique subjects reporting, if a subject reported more than one AE that was coded to the same SOC or PT, the subject will be counted only once for that specific SOC or PT.

The following summaries of AEs will also be provided:

- AEs by SOC and PT
- Treatment-related AEs by SOC and PT
- AEs by SOC, PT and maximum severity
- AEs by SOC, PT and causality relationship
- Serious AEs by SOC and PT
- Serious treatment-related AEs by SOC and PT
- AEs leading to study withdrawal by SOC and PT
- TEAEs leading to study drug discontinuation by SOC and PT
- AEs leading to death by SOC and PT

For AEs presented by relationship to study treatment, the strongest relationship to study treatment(s) during the clinical trial will be presented for each subject if coded to the same SOC or PT. For AEs presented by severity, the worst severity during the clinical trial will be presented for each subject if coded to the same SOC or PT. If either relationship or severity is missing, then the strongest relationship (related) or worst severity (severe) will be assigned.

This document is confidential.

10.4. Laboratory Evaluations

Blood samples for hematology, chemistry, and urine samples for urinalysis are to be collected at screening, Baseline, Weeks 2, 4, 6, 8, 12, 16, and 20 visits. All results will be provided using International System of Units (SI).

Descriptive statistics for hematology, chemistry, and urine will be provided for each test parameter and for change from baseline summarized by visit and treatment group. Shift tables (i.e., low-normal-high at Baseline versus low-normal-high at each post-baseline visit in a 3-by-3 contingency table) will be provided for hematology, biochemistry, and urine to assess changes from Baseline in laboratory values by visit and by treatment group. Listings of abnormal laboratory values, defined as values that are either $<0.5x$ lower limit of normal (LLN) or $>2x$ upper limit of normal (ULN) for each hematology and chemistry test parameter will be provided.

Boxplots for the change from baseline values for each post-baseline visit for hematology, chemistry and urinalysis (numerical results only) test parameters will be generated by treatment group, with LLN, ULN, $0.5x$ LLN and $2x$ ULN values plotted for each test parameter.

Separate listings of all laboratory data will be provided for all laboratory evaluations (hematology, biochemistry, and urinalysis).

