¹⁵ Subjects who develop influenza-like illness symptoms should have a rapid influenza diagnostic test (RIDT) done. Subjects with a positive RIDT should receive anti-influenza treatment per local standard of care, unless contraindicated, and/or other appropriate medical care.

¹⁶ Subjects who develop a productive cough that is new or a change from their normal baseline should have a sputum gram stain and culture sent for analysis.

¹⁷ At the Week 4 (or Week 6 if applicable) visit, only subjects participating in the PK analysis will get blood samples drawn for biomarkers. In these subjects, biomarker samples should be obtained 4 hours post-dose (see SOM and Lab Manual for instructions). If PK sampling cannot be performed at the Week 4 visit for logistical reasons, it should be collected at the Week 6 visit instead, but according to the schedule described above for Week 4, and this applies to timing of biomarker samples originally scheduled for Week 4 as well.

^{18a} At Weeks 4 (or Week 6 if applicable) and 12, subjects participating in the PK analysis will not take their study drug at home and instead will take their study drug at the study site.

^{18b} Subjects participating in the PK analysis should have their Week 8 visit scheduled approximately 7 hours after they take their study medication at home.

¹⁹ If clinically indicated, samples for Hematology, Chemistry and/or Urinalysis may be obtained at the Clinically Symptomatic Respiratory Illness Visit (Unscheduled).

²⁰ At Week 48, a long-term follow-up questionnaire will be administered by telephone to collect information regarding any hospitalizations, skilled nursing facility admissions and/or death since the Week 20 Visit.

²¹ If serum cotinine testing is unavailable, urine cotinine may be assessed in lieu of serum cotinine.

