6.8.5. Laboratory Evaluations

In the case where a laboratory assessment that is listed in the inclusion/exclusion criteria is outside of a **protocol-specified range** at Screening, the assessment may be repeated once prior to randomization for the purpose of inclusion and to rule out laboratory error. If the repeat value remains outside of protocol-specified ranges at the Baseline visit, the subject is excluded from the study.

In the case where a laboratory range is not specified by the protocol but is outside the reference range for the laboratory at Screening, a decision regarding whether the result is of clinical significance or not shall be made by the Investigator and shall be based, in part, upon the nature and degree of the observed abnormality. The assessment may be repeated once prior to randomization for the purpose of inclusion and to rule out laboratory error.

In all cases, the Investigator must document in the source documents, the clinical considerations (i.e., result was/was not clinically significant and/or medically relevant) in allowing or disallowing the subject to be enrolled in the study.

Clinically relevant deviations of laboratory test results occurring during or at completion of the study should be evaluated for criteria defining an AE and reported as such if the criteria are met. Repeated evaluations are mandatory until normalization of the result(s) or until the change is no

longer clinically relevant. In case of doubt, the Sponsor Medical Monitor or designee should be contacted.

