9.4.3.3. Clinical Laboratory Evaluations

Laboratory data will be analyzed quantitatively and qualitatively. The latter will be done via comparison of laboratory data to their reference ranges. Values outside the reference range as well as values defined as clinically relevant will be highlighted in the listings. Treatment groups will be compared descriptively with regard to distribution parameters as well as with regard to frequency and percentage of subjects with abnormal values or clinically relevant abnormal values. Furthermore, laboratory data will be evaluated longitudinally; changes from baseline in laboratory parameters will be compared between RTB101 10 mg and placebo.

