7.1. General Methods

All analyses and outputs will be produced using SAS® version 9.4 or later. Unless otherwise specified, efficacy and safety summaries will be presented for each treatment. All other summaries will be presented for each treatment and overall. Continuous variables will be summarized using the number of observations (n), mean, standard deviation (SD), median, minimum, and maximum. Categorical variables will be summarized using number of observations (n), frequency, and percentages of subjects.

All relevant subject data will be included in listings. All randomized subjects entered into the database will be included in subject data listings. All by visit summaries will use the nominal visit. Unscheduled visits will not be summarized but will be included in the listings.

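### No table counts subjects by arm with a marked laboratory value (<0.5x LLN or >2x ULN) at any time after Baseline, and unscheduled post-baseline values enter no laboratory summary

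*SAP*

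**What the plan says.** Protocol 9.4.3.3 says the arms will be compared descriptively on the "frequency and percentage of subjects with abnormal values or clinically relevant abnormal values". The unit is the subject, and clinically relevant abnormality is named separately from ordinary abnormality.

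SAP 10.4 plans four kinds of laboratory output:

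- descriptive statistics and change from Baseline, by visit;
- shift tables, specified as "low-normal-high at Baseline versus low-normal-high at each post-baseline visit in a 3-by-3 contingency table";
- boxplots of change from Baseline by visit, with lines at LLN, ULN, 0.5x LLN and 2x ULN;
- listings: one set of all laboratory data, and for hematology and chemistry "Listings of abnormal laboratory values, defined as values that are either" below 0.5x LLN or above 2x ULN.

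The index in SAP 15 agrees. Tables 14.3.4.1.1.2 and 14.3.4.1.2.2, which hold the marked values, are both titled as listings.

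SAP 7.1 adds: "Unscheduled visits will not be summarized but will be included in the listings". SAP 7.4 uses no visit windows, so an unscheduled value is not assigned to a nearby scheduled visit. SAP 12 records no change from the Protocol on laboratory analyses.

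**The concern.** Two things do not line up. First, the SAP defines a marked threshold of its own but never turns it into a count of subjects per arm. Its shift tables stop at low, normal and high, one visit at a time.

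Second, the Protocol creates unscheduled draws at moments when a laboratory signal is plausible. Under Protocol 5.5.2, "Subjects who permanently discontinue study drug due to an AE should return to the study site as soon as possible for an unscheduled visit", and that visit includes safety labs. Table 6-1 footnote 19 allows labs at the unscheduled respiratory illness visit, and Protocol 6.8.5 makes repeat testing mandatory after a clinically relevant deviation. Post-baseline values from unscheduled visits reach the listings but no shift table, by-visit summary or boxplot.

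At stake is one descriptive safety statement: how many subjects on each arm ever had a marked value. Protocol 3.3 names cytopenias, hyperglycemia and liver test elevations as risks known from high-dose use. It reports no increase at 10 mg once daily in the two earlier trials in elderly subjects (53 + 176 = 229 subjects). This trial adds about 533 on active drug, so the count is worth presenting directly.

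**Working it through.** The plan gives no figure on this point, so there is nothing to reproduce. The check is a comparison of texts, plus one illustration.

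**Step 1: count the index entries.** Laboratory entries in the SAP table index:

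| Entries | Type | Number |
|---|---|---|
| 14.3.4.1.1.1, 14.3.4.1.2.1 | summary by visit | 2 |
| 14.3.4.1.1.2, 14.3.4.1.2.2 | listing of marked values | 2 |
| 14.3.4.1.1.3, 14.3.4.1.2.3, 14.3.4.1.3.1 | shift, Baseline to each visit | 3 |

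That is 2 + 2 + 3 = 7, of which 0 give n (%) at the marked threshold or by worst post-baseline value. The separate figure and listing indexes add three sets of boxplots and three full listings, which give no n (%) either.

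**Step 2: can the by-visit tables stand in?** There are 7 scheduled post-baseline draws (Weeks 2, 4, 6, 8, 12, 16, 20). If k subjects in an arm are out of range at each one, the number ever out of range lies between k (the same people each time) and 7k (different people each time). The values of k below are assumed, for an arm of 533:

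| k per visit | Lower bound | Upper bound, 7k |
|---|---|---|
| 5 | 5 (5/533 = 0.9%) | 35 (35/533 = 6.6%) |
| 11 | 11 (2.1%) | 77 (14.4%) |
| 27 | 27 (5.1%) | 189 (35.5%) |

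A by-visit table cannot say where in such a range the trial falls. This concerns the ordinary low/high categories, since the shift tables have no marked category. It shows what by-visit counts leave open and does not forecast results.

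**Step 3: what reaches the AE tables?** Protocol 6.8.5 says: "Clinically relevant deviations of laboratory test results occurring during or at completion of the study should be evaluated for criteria defining an AE". Protocol 7.1 makes a laboratory value an AE if it causes signs or symptoms, is judged clinically significant or needs therapy. A numeric rule applies only to ALT, AST and total bilirubin above 3x ULN, which must be reported as Grade 3 AEs. Protocol 6.8.5.1 and 6.8.5.2 name 10 hematology and 13 chemistry parameters, so 3 of 23 have such a rule. This counts rules, not subjects. For the other 20, entry to the AE tables depends on the investigator's judgment and not on the <0.5x LLN or >2x ULN limits.

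**Step 4: scope of the unscheduled rule.** An unscheduled repeat before the first dose can still serve as Baseline under SAP 7.2.4 (last measurement before dosing). The exclusion therefore bears on post-baseline values only.

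**The case against.** The strongest reply is that the information is not lost. The marked-value listings are filtered to the threshold, include unscheduled visits and, under SAP 13.2.5.3, are sorted by treatment group and then subject. A reader can count subjects per arm from them. That stands: what is missing is a tabulated count with its denominator and percentage.

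It can also be said that Protocol 9.4.3.3 is largely met. Shift tables cover abnormal values by arm. Clinically relevant values should become AEs, which SAP 10.3 tabulates as unique subjects with percentages. The Protocol section mentions neither worst values nor the 0.5x and 2x limits, and no document equates those limits with clinical relevance. This also stands in large part, so a reader who infers that the SAP breaks the Protocol's commitment goes further than the text allows.

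On unscheduled draws, the visit after stopping drug follows an AE that is already counted, and a repeat test follows a deviation already found. Liver values above 3x ULN are AEs whenever they occur, and Protocol 5.5.5 sends two or more such subjects to unblinded DMC review. An inference that serious laboratory toxicity could go unseen is therefore not supported. There is also a fair reason to leave unscheduled values out: subjects with more visits have more chances of an extreme value.

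Two further inferences fail. SAP 10.6 groups QTc into five threshold categories, but its index table (14.3.4.2.3) is by visit. It supports tabulating threshold categories, not worst-value counting. The word Grade in the three shift-table titles does not make them toxicity-graded, because SAP 10.4 defines the categories as low, normal and high.

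**Conclusion.** The point holds as a minor descriptive-safety gap. The SAP sets a marked-abnormality threshold and gives no by-arm number and percentage of subjects who cross it. It also leaves post-baseline unscheduled values out of every laboratory summary. Listings, boxplot lines and AE tables cover part of the ground, but none presents that count.

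No efficacy conclusion, alpha level or power figure is affected. The size in subjects is unknown: the documents give no rate of marked values and no number of unscheduled draws, and the ranges in the working rest on assumed per-visit counts. The textual finding rests on SAP 7.1, 10.4 and 15 as written and needs no assumption about results. This is a cheap improvement and not a defect that would change how the trial is read.

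**What to change.** Add two tables to SAP 10.4 and the index, one for hematology and one for chemistry. For each parameter, give by-arm n (%) of Safety Set subjects whose worst post-baseline value is <0.5x LLN or >2x ULN. The denominator is subjects with at least one post-baseline value. State in one sentence that unscheduled and repeat values count toward the worst value, as an exception to SAP 7.1.

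A >3x ULN row for ALT, AST and total bilirubin is optional, since it would largely repeat the mandatory Grade 3 AEs. Retitling the three Grade shift tables as low/normal/high is editorial.

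The cost is two descriptive tables from data already collected. Some rows may be all zero. Because subjects with more visits contribute more draws, the tables should be read beside the by-visit summaries.
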